13.8. Sample Size Considerations

As we recognize that not all participants may complete the study, a dropout rate of 10% is assumed for all sample size calculations provided below.

It is assumed that the true mean percent reduction from baseline in mean gastric eosinophil counts when treated with dupilumab will be at least 50%. This is a conservative estimate based on the efficacy of dupilumab in EoE patients; dupilumab reduced the mean (least square) peak esophageal eosinophil count by -94/HPF (9.5 standard error; n=23) and -7.4 (9.6 standard error; n=24) in the placebo group in a recent study of EoE¹³. At Week 12, dupilumab versus placebo significantly reduced peak eosinophil counts from baseline (-92.9% vs +14.2%; P<0.0001). It is also assumed that the true mean percent reduction from baseline in mean eosinophil counts for the placebo group will be at most 25% and we expect it to be much less as the placebo effect in EoE was 14% increase in eosinophil levels as noted above. Assuming a standard deviation of 25 percentage units, a sample size of 20 participants per treatment group will provide at least 80% power to detect a true absolute difference in percent reduction from baseline in mean eosinophil counts of 23% at alpha = 0.05. If we assume that the dropouts from the dupilumab arm have a mean reduction in eosinophil counts similar to those on placebo (25%) then we would expect 48% decline in eosinophil count among those in the dupilumab arm, thus we are sufficiently powered even with dropouts. A sample size of 20 per treatment group will also provide at least 80% power to detect a difference in the proportions of participants with induction of disease remission of 42 percentile points (e.g. 62% vs. 20%) at the two-sided 5% level of significance. Notably, if 2 individuals in the dupilumab arm drop out then the effective disease remission rate would be 67% among those completing the study in order to obtain a 62% overall remission rate for the dupilumab arm.

14. Identification and Access to Source Data

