13.5.2. Primary Analysis of Primary Endpoint

The primary outcome measure will be the relative change from baseline from week 0 to week 12 in the mean of the eosinophil counts from the 5 worst microscopic fields in the gastric antrum and/or body in the intent to treat population. Relative change is defined as (week 12 – baseline)/baseline. Regression analyses will be performed with the primary outcome measure as the dependent variable and treatment group as the independent variable. Appropriate transformations, such as a log-transformation, may be used to satisfy the distributional assumptions prior to model fitting. If there are continued concerns about data distributions, equivalent nonparametric tests will be employed. To ensure that immunosuppression (e.g. corticosteroid, swallowed glucocorticosteroids for EG (Entocort), or immunosuppressive agents) use does not influence results, we will also perform regression analyses with corticosteroid/immunosuppression therapy as a covariate (including considering binary (y/n), and dose (none, low, high). Statistical testing will be performed at the two-sided 5% level of significance.

Because we will be using an intent to treat model, all individuals completing study visit 1 will be included in the analysis of the primary outcome including participants receiving steroids within the last 30 days before endoscopy. Because early termination/withdrawal of the study is possible, missing outcome data must be imputed. First, we will evaluate the patterns of missing data to help us understand whether the data may be missing at random. Specifically, we will review patient drop out reasons and baseline patient characteristics. We will then use multiple imputation which will allow us to handle the data whether missing at random or missing not at random, leveraging the longitudinal data collected. Factors to be considered in the multiple imputation are the prior eosinophil counts, participant clinical characteristics and longitudinal secondary outcomes.

To ensure the robustness of our missing data approach, analyses will also be conducted among participants that completed the study at 12 weeks (per protocol) as sensitivity analysis. If differences occur between the results of the two analyses, we will explore the data to understand the pattern of missingness, using tipping point analysis to understand the impact of the missing data on inference, and consider additional imputation or utilize longitudinal data analyses.

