13.5.4. Analyses of Secondary and Other Endpoints

For the secondary and exploratory outcome measures related to differences between the arms of the study, generalized linear mixed effects models will be used with the appropriate distribution function and link function (e.g. binomial distribution and logit link for binary outcomes, normal distribution and identity link for normally distributed continuous outcomes). Appropriate transformations may be used to satisfy the normality assumptions of the model, if needed. Baseline corticosteroid/immunosuppressive therapy use will be included as a covariate in the models. Study site will be included as a random effect in the models. To evaluate factors associated with drug responsiveness, we will use generalized linear mixed models as described above but restrict the analyses to those in the medication arm of the study. Statistical testing will be performed at the two-sided 5% level of significance.

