13.7. Statistical Hypotheses

Primary Endpoint: the percent change from baseline from week 0 to week 12 in the mean of the eosinophil counts from the 5 worst microscopic fields in the gastric antrum and/or body

$$H_0: b_1 = b_{1,0}$$

$$H_A: b_1 \neq b_{1,0}$$

Where b_1 is the coefficient for treatment status from the linear model and $b_{1,0}$ is zero.

Key secondary endpoint: We have secondary endpoints (Patient global impression of severity (PGI-S), Patient global impression of change (PGI-C), Proportion of participants achieving threshold response < 30 eos/hpf in 5 hpfs, Eosinophilic Gastritis Endoscopy Assessment (EG-REFS), Eosinophilic Gastritis Symptom Questionnaire (EG-SQ).

$$H_0: b_1 = b_{1,0}$$

$$H_A: b_1 \neq b_{1,0}$$

Where b_1 is the coefficient for treatment status from the linear model and $b_{1,0}$ is zero.

For both primary and secondary endpoints, the type of comparison is superiority.

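### Does rounding 47.5% to 48% in the dropout check, or the choice of test for remission, undo the 80% power stated for 40 participants?

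*Protocol*

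**What the plan says.** Protocol 13.8 makes three linked statements; the SAP repeats the paragraph under Sample Size Considerations.

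- Primary endpoint: "Assuming a standard deviation of 25 percentage units, a sample size of 20 participants per treatment group will provide at least 80% power" for a true difference of 23 points in percent reduction, at alpha 0.05. The planning means are at least 50% on dupilumab and, on placebo, "at most 25% and we expect it to be much less as the placebo effect in EoE was 14% increase".
- Dropout: 10% is assumed. If dupilumab dropouts have the placebo mean, "then we would expect 48% decline in eosinophil count among those in the dupilumab arm, thus we are sufficiently powered even with dropouts".
- Remission: 20 per group gives "at least 80% power to detect a difference in the proportions of participants with induction of disease remission of 42 percentile points", with 62% against 20% as the example. If two dupilumab participants drop out, "the effective disease remission rate would be 67% among those completing the study".

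No test or formula is named behind either power figure. On the analysis side, Protocol 13.5.2 says "Regression analyses will be performed with the primary outcome measure as the dependent variable and treatment group as the independent variable", and Protocol 13.7 states the hypothesis on a parameter that "is the coefficient for treatment status from the linear model". Binary endpoints fall under Protocol 13.5.4: a generalized linear mixed model with "binomial distribution and logit link for binary outcomes", a covariate for baseline corticosteroid or immunosuppressant use, and a random site effect.

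**The concern.** The dropout sentence appears to close the argument exactly: 48 minus 25 is 23, the difference said to carry at least 80% power. Without rounding it is 22.5, which is below 23, so read strictly the inference to adequate power does not follow from the paragraph's own numbers. With one treatment term, the planned linear model amounts to a two-sample t test on 38 degrees of freedom, and that test falls just under 80% at 22.5 points.

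The remission claim is worded as a floor, yet chi-square and an unadjusted logistic model both land below it.

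This paragraph is the only quantitative justification for 40 participants. If the errors were large, the trial would be smaller than its stated aims require.

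**Working it through.** **Inputs (Protocol 13.8).** Two-sided 5%, SD 25 points, 20 per arm, dupilumab 50%, placebo 25%, dropout 10%; remission 62% against 20%.

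**1. The plan's primary figure.** Standard error = 25 × √(2/20) = 7.906. At 23 points the noncentrality is 23/7.906 = 2.91 and the critical t on 38 df is 2.024. Power is 80.9% (82.9% by the normal approximation). The stated figure reproduces.

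**2. The dropout scenario.** Mean = 0.9 × 50 + 0.1 × 25 = 47.5. Difference = 47.5 − 25 = 22.5. Noncentrality = 22.5/7.906 = 2.85.

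| Method | Power at 22.5 points | Difference needed for 80% |
|---|---|---|
| t test, 38 df | 79.2% | 22.73 |
| Normal approximation | 81.2% | (1.960 + 0.842) × 7.906 = 22.15 |

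The t test would need 21 per arm instead of 20. Holding the SD at 25 slightly favours the plan: with exactly 2 of 20 dupilumab values centred on the placebo mean, simulated t-test power is 78.0%.

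**3. How sensitive this is.** In general the diluted difference is 0.9 × (50 − placebo reduction). Power of 80% needs a placebo reduction of at most 50 − 22.73/0.9 = 24.7%. At 20% the difference is 0.9 × 30 = 27 points and power is 91.4%.

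**4. The analysis now planned as primary.** The SAP (Definitions of Patient Populations; Statistical Analysis Changes From the Protocol) reports complete-case ITT as primary. Dropouts then leave the analysis and do not dilute the mean, so the difference stays at 25 points:

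- 18 per arm: 83.0%
- 20 against 19, as with the single placebo dropout the SAP reports and assuming 40 randomised: 86.0%

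**5. Remission, 62% against 20%, 20 per arm.**

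- Arcsine: h = 2·asin√0.62 − 2·asin√0.20 = 0.886; Φ(0.886 × √10 − 1.960) = 80.0% (0.7999).
- Pooled normal, mean proportion 0.41: Φ[(0.42 × √20 − 1.960 × √(2 × 0.41 × 0.59)) / √(0.62 × 0.38 + 0.20 × 0.80)] = Φ(0.819) = 79.4%.
- Unpooled normal: Φ(0.42/√(0.3956/20) − 1.960) = 84.8%, where 0.3956 = 0.62 × 0.38 + 0.20 × 0.80.
- Exact enumeration: chi-square 79.1%, likelihood ratio 79.1%, unadjusted logistic Wald 75.8%.
- Logistic model with one null binary covariate (25% prevalence assumed, 10,000 simulations): Wald 77.2%, likelihood ratio 82.1%.

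The plan's 67% among completers also reproduces: (62 − 0.1 × 20)/0.9 = 66.7%. Enumeration at 67% against 20% with 18 per arm gives 87.0% (chi-square), 87.2% (likelihood ratio) and 85.1% (Wald).

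**The case for a change.** The best case for a correction is that the rounding falls at the decisive step. It lifts the difference from just under the plan's own threshold to exactly that threshold, and the next words conclude that power is adequate. Under the planned t test the exact figure is below 80%, and only the normal approximation rescues it. Allowing for the larger spread in a mixed arm takes it to 78.0%. For remission, a claim of at least 80% is a floor, and chi-square, the likelihood ratio, the pooled normal formula and the unadjusted Wald test all fall under it. Rewording three figures would cost almost nothing.

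The arithmetic in that case stands: 47.5 is not 48, and 79.2% is the right t-test power at 22.5 points. The inference from it does not. The plan attaches 80% to 23 points, where it is correct, and attaches no power figure to the dropout scenario; calling 79.2% sufficient is a fair description.

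On remission, the documents name no test, and ordinary planning formulas run from 79.4% to 84.8%. The 75.8% comes from an unadjusted Wald test, whereas the planned model carries a steroid or immunosuppressant covariate and a site effect (tested first under the SAP). With one covariate the simulated range of 77% to 82% includes 80%. Stricter tests do fall well short (Fisher's exact 69.5%), but neither document plans Fisher's test for this endpoint.

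**Conclusion.** No change follows. The primary power figure is right as stated (80.9% at 23 points). The dropout sentence contains a whole-number rounding worth 0.5 point of difference and, by t test, leaves power 0.8 percentage point under 80%. That shortfall exists only if the dupilumab reduction is exactly its stated minimum and the placebo reduction is between 24.7% and its 25% ceiling. An SD of 25 is itself a round assumption, so differences of this size are within planning precision. The scenario also does not match the SAP's complete-case primary analysis, for which power is 83.0% to 86.0% at the planning means.

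The remission figure is about 80% by common planning formulas and has not been shown to be wrong under the covariate-adjusted model. It would have been tidier to print 47.5% and name the test behind each figure, but doing so alters no sample size, analysis set, test or interpretation. These results rest on the plan's own SD, means and dropout rate, a two-sided 5% level, 20 per arm and, for the simulated logistic model, one covariate with no effect and an assumed 25% prevalence.

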14.1. Source Data

Source documents and source data are considered to be the original documentation where participant information, visits consultations, examinations and other information are recorded. Documentation of source data is necessary for the reconstruction, evaluation and validation of clinical findings, observations and other activities during a clinical trial. All source documents must be kept on file with the CRFs (CRFs may be either paper or electronic [eCRF]). Data will be entered into a database that complies with all applicable guidelines.

14.2. Access to Source Data

The site investigators and site staff will make all source data available to the DAIT/NIAID, IPM, study sponsor ([name]) as well as to relevant health authorities such as the FDA. Authorized representatives as noted above are bound to maintain the strict confidentiality of medical and research information that may be linked to identified individuals.

14.3 Data Collection and Management Responsibilities

Data collection is the responsibility of the study staff at the site under the supervision of the site principle Investigator. The Investigator is responsible for ensuring the accuracy, completeness, legibility, and timeliness of the data reported. All source documents should be completed in a neat, legible manner to ensure accurate interpretation of data.

The DMCC will develop, test, and maintain the data capture system using a web-based data collection system, REDCap, as the primary source of data entry and storage. REDCap is a software toolset and workflow methodology for electronic collection and management of research and clinical trial data developed by Vanderbilt University. The REDCap system provides a secure, web-based application that is flexible and provides: 1) an intuitive interface for users to enter data and have real time validation rules (with automated data type and range checks) at the time of entry; 2) HIPAA-compliant and 21 CFR Part 11-ready audit trails for tracking page views, data manipulation and export procedures; 3) record locking and electronic signature functions; 4) fine grained control of user rights to view and manipulate data, and tool to sequester data access for multiple sites; 5) a report builder for reporting, monitoring and querying patient records; and 6) automated export procedures for seamless data downloads to common statistical packages (SPSS, SAS, Stata, R/S-Plus). Study data will be entered into REDCap, supported by the DMCC. The REDCap system complies with all applicable guidelines to ensure patient confidentiality, data integrity, and reliability. All data management best practices including quality controls and data validation procedures will be applied to ensure the validity and accuracy of the clinical database. A data management plan will be developed which will describe the data collection process, database development, quality control processes and reporting.

15. Quality Assurance and Quality Control

15.1. Training of study site personnel

All study staff listed on the site delegation log must be trained on the conduct of the study before engaging in any study-related activities.

15.2. Monitoring of the study

The funding agency and/or the Principle Investigator will designate a study monitor who will review the study site prior to enrollment of the first patient, and periodically throughout the study. The monitor will compare CRF entries with the corresponding source documents, as outlined in the ICH guidelines. The study monitor may also review participant informed consent forms (ICFs), patient recruitment and follow-up documentation, AEs, SAEs, and concomitant therapy; along with records of dispensation of study drug, compliance, and accountability. A copy of the drug dispensing log must be provided to the sponsor upon request.

15.3. Audits and inspections

The study PI, funding agency or Cincinnati Children's Hospital Medical Center (CCHMC) representative may subject this trial to quality assurance audits or inspections at any time. In the case of an audit or inspection, the investigator is responsible for the following:

- Informing the sponsor of a planned inspection by regulatory agencies as soon as they become aware of the inspection, and authorizing the sponsor to participate in the inspection
- Providing access to all necessary facilities, study data, and documents for the inspection or audit
- Immediately communicating any information arising from inspection by regulatory agencies to the sponsor
- Taking all appropriate measures requested by the sponsor to resolve any problems discovered during audit or inspection

Documents subject to audit or inspection include, but are not limited to:

- all source documents, paper CRFs, and ICFs
- medical records
- correspondence
- IRB/EC files
- documentation of certification and quality control of supporting laboratories
- records relevant to the study maintained in any supporting pharmacy facilities.

Study material storage data are also subject to inspection. Representatives of CCHMC may observe the conduct of any aspect of the trial or its supporting activities both within and outside of the investigator's institution. In all instances, the confidentiality of the data must be respected.

Quality control (QC) procedures will be implemented beginning with the data entry system and data QC checks that will be run on the database will be generated. Any missing data or data anomalies will be communicated to the site(s) for clarification/resolution.

The investigational site will provide direct access to all trial related sites, source data/documents, and reports for the purpose of monitoring and auditing by the sponsor, and inspection by local and regulatory authorities.

16. Protocol Deviations

16.1. Protocol Deviation Definitions

Protocol Deviation – The investigators and site staff will conduct the study in accordance to the protocol; no deviations from the protocol are permitted. Any change, divergence, or departure from the study design or procedures constitutes a protocol deviation. As a result of any deviation, corrective actions will be developed by the site and implemented promptly.

Major Protocol Deviation (Protocol Violation) - A Protocol Violation is a deviation from the IRB approved protocol that may affect the participant's rights, safety, or well-being and/or the completeness, accuracy and reliability of the study data. In addition, protocol violations include willful or knowing breaches of human subject protection regulations, or policies, any action that is inconsistent with the NIH Human Research Protection Program's research, medical, and ethical principles, and a serious or continuing noncompliance with federal, state, local or institutional human subject protection regulations, policies, or procedures.

Non-Major Protocol Deviation - A non-major protocol deviation is any change, divergence, or departure from the study design or procedures of a research protocol that does not have a major impact on the participant's rights, safety or well-being, or the completeness, accuracy and reliability of the study data.

16.2. Reporting and Managing Protocol Deviations

The study site principal investigator has the responsibility to identify, document and report protocol deviations as directed by the study Sponsor. However, protocol deviations may also be identified during site monitoring visits or during other forms of study conduct review, including processing of data at the Data Center. Upon determination that a protocol deviation has occurred, the study staff will a) notify the site Principal Investigator, b) notify the NIAID Project Manager, and c) will complete a Protocol Deviation form. The DAIT Project Manager will review and approve the correction action plan that is to be implemented as a result of the protocol deviation will make the final decision as to whether the Deviation is major or not. The study sponsor ([name], PhD will submit the Protocol Deviation reports to the appropriate review bodies (IRB, DSMB, FDA etc.). Ethical Considerations and Compliance with Good Clinical Practice.

17. Ethics and regulatory review

Before study initiation, the protocol and the informed consent documents will be reviewed and approved by the Cincinnati Children's Hospital Medical Center IRB (CCHMC IRB) which will work as a central IRB (following reliance agreements from each site).

17.1. Statement of Compliance

This clinical study will be conducted using good clinical practice (GCP), as delineated in Guidance for Industry: E6 Good Clinical Practice Consolidated Guidance, and according to the criteria specified in this study protocol. Before study initiation, the protocol and the informed consent documents will be reviewed and approved by the IRB. Any amendments to the protocol or to the consent materials will also be approved by the IRB before they are implemented.

17.2. Informed Consent Process

The Principal Investigator will designate appropriate study staff for performing the informed consent process. During the consent process, study staff will provide information about the study to a prospective participant and will allow adequate time for review and discussion prior to his/her decision. The principal investigator or trained clinical research staff listed on the delegation log will review the consent and answer questions. The prospective participant will be told that being in the trial is voluntary and that he or she may withdraw from the study at any time, for any reason. All participants (or their legally authorized representative) will read, sign, and date a consent form before undergoing any study procedures. Consent materials will be presented in participants' primary language. A copy of the signed consent form will be given to the participant.

This study will be conducted in compliance with ICH E6 GCP: Consolidated Guidelines pertaining to informed consent. At the first visit, prior to initiation of any study-related procedures, participants will give their written consent to participate in the study after having been informed about the nature and purpose of the study, participation/termination conditions, and risks and benefits. The informed consent document must be signed and dated by the participant, prior to study participation. A copy of the informed consent document must be provided to the participant. Signed consent forms must remain in the participant's study file and be available for verification by the monitor, IRB, and/or regulatory authorities at any time.

The consent form will be revised when important new safety information is available, the protocol is amended, and/or new information becomes available that may affect participation in the study.

